APPENDIX 2. PARTIAL DATE CONVENTIONS

Imputed dates will not be presented in the listings. In the algorithms for date, SEP-4199 study med start date the date of first dose of study drug.

ALGORITHM FOR ADVERSE EVENTS:

The concept of "date" below should also include time information whenever available.

START DATE	STOP DATE	ACTION
Known	Known	If start date < SEP-4199 study med start date, then pre-treatment events If start date >= SEP-4199 study med start date, then SEP-4199 AE
Known	Partial	If start date < SEP-4199 study med start date, then pre-treatment events If start date >= SEP-4199 study med start date, then SEP-4199 AE
Known	Missing	If start date < SEP-4199 study med start date, then pre-treatment events If start date >= SEP-4199 study med start date, then SEP-4199 AE
Partial, but known components show that it cannot be on or after SEP-4199 study med start date	Known	Pre-treatment events
Partial, but known components show that it cannot be on or after SEP-4199 study med start date	Partial	Pre-treatment events
Partial, but known components show that it cannot be on or after SEP-4199 study med start date	Missing	Pre-treatment events
Partial	Partial	Impute stop date as latest possible date (ie, last day of month if day unknown or 31st December if day and month are unknown). Then: If stop date < SEP-4199 study med start date, then pre-treatment events If stop date >= SEP-4199 study med start date, then SEP-4199 AE

Document:

Author:

Version Number:

V2.0

Version Date:

21MAY2020

Template No: CS_TP_BS016 Revision 4
 Effective Date: 01Apr2016

Reference: CS_WI_BS005

START DATE	STOP DATE	ACTION
Partial, could be on or after SEP-4199 study med start date	Known	If stop date < SEP-4199 study med start date, then pre-treatment events If stop date >= SEP-4199 study med start date, then SEP-4199 AE
Partial, could be on or after SEP-4199 study med start date	Partial	Impute stop date as latest possible date (ie, last day of month if day unknown or 31st December if day and month are unknown). Then: If stop date < SEP-4199 study med start date, then pre-treatment events If stop date >= SEP-4199 study med start date, then SEP-4199 AE
Partial	Missing	Assumed SEP-4199 AE
Missing	Known	If stop date < SEP-4199 study med start date, then pre-treatment events If stop date >= SEP-4199 study med start date, then SEP-4199 AE
Missing	Partial	Impute stop date as latest possible date (ie, last day of month if day unknown or 31st December if day and month are unknown). Then: If stop date < SEP-4199 study med start date, then pre-treatment events If stop date >= SEP-4199 study med start date, then SEP-4199 AE
Missing	Missing	Assumed SEP-4199 AE

 Document:

Author:

Version Number:

V2.0

Version Date:

21MAY2020

 Template No: CS_TP_BS016 Revision 4
 Effective Date: 01Apr2016

Reference: CS_WI_BS005

ALGORITHM FOR PRIOR / CONCOMITANT / POST-TREATMENT MEDICATIONS:

The concept of "date" below should also include time information whenever available. Time will not be imputed.

START DATE	STOP DATE	ACTION
Known	Known	
If stop date < SEP-4199 study med start date, assign as prior.
 
If stop date >= SEP-4199 study med start date and start date <= end of treatment date (date of last dose of study drug), assign as concomitant.
 
If stop date >= SEP-4199 study med start date and start date > end of treatment (date of last dose of study drug), assign as post treatment.

Known	Partial	
Impute stop date as latest possible date:
 
 • If only day unknown, impute as the earlier of (last day of the month; date of the last study visit). • If month and day unknown, impute as the earlier of (31st December; date of the last study visit). 
Then:
 
If stop date < SEP-4199 study med start date, assign as prior.
 
If stop date >= SEP-4199 study med start date and start date <= end of treatment (date of last dose of study drug), assign as concomitant.
 
If stop date >= SEP-4199 study med start date and start date > end of treatment (date of last dose of study drug), assign as post treatment.

Known	Missing	
If stop date is missing could never be assumed a prior medication.
 
If start date <= end of treatment (date of last dose of study drug), assign as concomitant.
 
If start date > end of treatment (date of last dose of study drug), assign as post treatment.

Partial	Known	
Impute start date as earliest possible date:
 
CRF questions: 'Started prior to study?' = Yes; 'Started after last dose of study medication?' = No.
 
 • If only day unknown, impute as the later of (first day of the month; date of birth). • If month and day unknown, impute as the later of (1st January; date of birth). 
CRF questions: 'Started prior to study?' = No; 'Started after last dose of study medication?' = Yes.
 
 • If only day unknown, impute as the later of (first day of the month; end of treatment + 1). • If month and day unknown, impute as the later of (1st January; end of treatment + 1). 
CRF questions: 'Started prior to study?' = No; 'Started after last dose of study medication?' = No.
 
 • If only day unknown, impute as the later of (first day of the month; date of ICF). • If month and day unknown, impute as the later of (1st January; date of ICF). 
Then:
 
If stop date < SEP-4199 study med start date, assign as prior.
 
If stop date >= SEP-4199 study med start date and start date <= end of treatment (date of last dose of study drug), assign as concomitant.

Document:

Author:

Version Number:

V2.0

Version Date:

21MAY2020

Template No: CS_TP_BS016 Revision 4
 Effective Date: 01Apr2016

Reference: CS_WI_BS005

		If stop date \geq SEP-4199 study med start date and start date $>$ end of treatment (date of last dose of study drug), assign as post treatment.
Partial	Partial	
Impute start date as earliest possible date: CRF questions: 'Started prior to study?' = Yes; 'Started after last dose of study medication?' = No.
 
 • If only day unknown, impute as the later of (first day of the month; date of birth). • If month and day unknown, impute as the later of (1st January; date of birth). 
CRF questions: 'Started prior to study?' = No; 'Started after last dose of study medication?' = Yes.
 
 • If only day unknown, impute as the later of (first day of the month; end of treatment + 1). • If month and day unknown, impute as the later of (1st January; end of treatment + 1). 
CRF questions: 'Started prior to study?' = No; 'Started after last dose of study medication?' = No.
 
 • If only day unknown, impute as the later of (first day of the month; date of ICF). • If month and day unknown, impute as the later of (1st January; date of ICF). 
Impute stop date as latest possible date:
 
 • If only day unknown, impute as the earlier of (last day of the month; date of the last study visit). • If month and day unknown, impute as the earlier of (31st December; date of the last study visit). 
Then:
 
If stop date $<$ SEP-4199 study med start date, assign as prior. If stop date \geq SEP-4199 study med start date and start date \leq end of treatment (date of last dose of study drug), assign as concomitant. If stop date \geq SEP-4199 study med start date and start date $>$ end of treatment (date of last dose of study drug), assign as post treatment.

Partial	Missing	
Impute start date as earliest possible date: CRF questions: 'Started prior to study?' = Yes; 'Started after last dose of study medication?' = No.
 
 • If only day unknown, impute as the later of (first day of the month; date of birth). • If month and day unknown, impute as the later of (1st January; date of birth). 
CRF questions: 'Started prior to study?' = No; 'Started after last dose of study medication?' = Yes.
 
 • If only day unknown, impute as the later of (first day of the month; end of treatment + 1). • If month and day unknown, impute as the later of (1st January; end of treatment + 1). 
CRF questions: 'Started prior to study?' = No; 'Started after last dose of study medication?' = No.
 
 • If only day unknown, impute as the later of (first day of the month; date of ICF). • If month and day unknown, impute as the later of (1st January; date of ICF). 
Then:
 
If stop date is missing could never be assumed a prior medication. If start date \leq end of treatment (date of last dose of study drug), assign as concomitant. If start date $>$ end of treatment (date of last dose of study drug), assign as post

Document:

Author:

Version Number:

V2.0

Version Date:

21MAY2020

 Template No: CS_TP_BS016 Revision 4
 Effective Date: 01Apr2016

Reference: CS_WI_BS005

		treatment.
Missing	Known	If stop date < SEP-4199 study med start date, assign as prior. If stop date >= SEP-4199 study med start date, assign as concomitant
Missing	Partial	Impute stop date as latest possible date: 
 • If only day unknown, impute as the earlier of (last day of the month; date of the last study visit). • If month and day unknown, impute as the earlier of (31st December; date of the last study visit). Then: If stop date < SEP-4199 study med start date, assign as prior. If stop date >= SEP-4199 study med start date, assign as concomitant.
Missing	Missing	Assign as concomitant

 Document:

Author:

Version Number:

V2.0

Version Date:

21MAY2020

 Template No: CS_TP_BS016 Revision 4
 Effective Date: 01Apr2016

Reference: CS_WI_BS005

PARTIAL DATE IMPUTATION RULES FOR INITIAL ONSET OF BIPOLAR I DISORDER/CURRENT EPISODE OF MAJOR DEPRESSION ASSOCIATED WITH BIPOLAR I DISORDER SYMPTOMS:

For subjects with partial onset dates of bipolar I disorder/current episode, impute the onset date using the following rules:

- If only day unknown, impute as the earlier of: last day of the month, or date of ICF.
- If both month and day unknown, impute as the earlier of: 31st December of the year, or date of ICF.

Document:

Author:

Version Number:

V2.0

Version Date:

21MAY2020

Template No: CS_TP_BS016 Revision 4
Effective Date: 01Apr2016

Reference: CS_WI_BS005

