8. SELECTION OF SUBJECTS

8.1. Subject Inclusion Criteria

To qualify for study participation, the subject must meet all of the following inclusion criteria:

1. Subject is 18 to 65 years of age, inclusive, at the time of informed consent with bipolar I disorder, current episode depressed with or without rapid cycling disease course (≥ 4 episodes of mood disturbance but < 8 episodes in the previous 12 months) with or without psychotic features (diagnosed by DSM-5 criteria, and confirmed by the SCID-5-CT). The current episode of major depression associated with bipolar I disorder must be confirmed by the Investigator and noted in the source records.
2. Subject provides written informed consent and is willing and able to comply with the protocol in the opinion of the investigator.
3. Subject or legally acceptable representative must possess an educational level and degree of understanding of English or the local language that enables them to communicate suitably with the Investigator and the study coordinator.
4. Subject must have a lifetime history of at least one bipolar manic or mixed manic episode. It is strongly recommended that a reliable informant (eg, family member or caregiver) be available to confirm this history.
5. Subject's current major depressive episode is ≥ 4 weeks and less than 12 months in duration at Screening.
6. Subject has a MADRS total score ≥ 22 at both Screening and Baseline.
7. Subject has a YMRS total score ≤ 12 at Screening.
8. Female subjects of childbearing potential must have a negative serum β -hCG test at Screening.
9. Females who participate in this study must be one of the following:
 - Unable to become pregnant (eg, postmenopausal, surgically sterile, etc.)
 - Practicing abstinence or part of an abstinent lifestyle
 - Using and will continue to use a highly effective form of birth control for at least 28 days prior to administration of the first dose of study drug, during the treatment period, and 2 months after completion or premature discontinuation from the study drug. See [Section 10.4](#) for further information on acceptable methods of birth control.
10. Male subjects with partners of child bearing potential must be practicing abstinence, part of an abstinent lifestyle or using protocol-specified methods of birth control. See [Section 10.4](#) for further information on acceptable methods of birth control.

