- Time since initial onset of bipolar I disorder, in years, calculated relative to date of informed consent (see [APPENDIX 2](#) for partial date imputation rules)
- Time since onset of current episode of major depression associated with bipolar I disorder symptoms, in months, calculated relative to date of informed consent (see [APPENDIX 2](#) for partial date imputation rules)
- Frequency distribution of number of prior hospitalizations for Bipolar I depression (0, 1, 2, 3, and 4 or more)
- Frequency distribution of DSM-5 code in ascending numeric order
- Bipolar I diagnosis subtype (Bipolar I disorder without rapid Cycling and Bipolar I disorder with rapid cycling)
- Number and percentage of subjects with other psychiatric disorders
- Number and percentage of subjects with any other psychiatric disorders

Other psychiatric Disorder data will be summarized for SAF population in a separate table by summarizing Diagnosis and DSM-5 codes.

11.1.DERIVATIONS

- Time since initial onset of bipolar disorder (years):

(Date of informed consent – date of initial onset of bipolar disorder) / 365.25

- Time since initial onset of current episode of major depression (months):

(Date of informed consent – date of initial onset of current episode of major depression) / 30.25

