0.1 Did not satisfy important inclusion or exclusion criteria

Subjects who did not satisfy one or more of the following eligibility criteria at screening and/or at baseline will be considered IPDs whether or not an exemption was granted during the study. Subjects who violated one or more of the below criteria will be identified programmatically based on the data recorded on the Inclusion/Exclusion Criteria CRF pages, and presented in a data listing.

In addition, supporting data are available to facilitate programmatic or manual identification of violations of the above criteria. These supporting data will also be presented in data listings.

INCLUSION CRITERIA

- I.1 Subject is 18 to 65 years of age, inclusive, at the time of informed consent with bipolar I disorder, current episode depressed with or without rapid cycling disease course (≥ 4 episodes of mood disturbance but < 8 episodes in the previous 12 months) with or without psychotic features (diagnosed by DSM-5 criteria, and confirmed by the SCID-5-CT). The current episode of major depression associated with bipolar I disorder must be confirmed by the Investigator and noted in the source records.
- I.2 Subject provides written informed consent and is willing and able to comply with the protocol in the opinion of the investigator.
- I.3 Subject or legally acceptable representative must possess an educational level and degree of understanding of English or the local language that enables them to communicate suitably with the Investigator and the study coordinator.
- I.4 Subject must have a lifetime history of at least one bipolar manic or mixed manic episode. It is strongly recommended that a reliable informant (eg, family member or caregiver) be available to confirm this history.
- I.5 Subject's current major depressive episode is ≥ 4 weeks and less than 12 months in duration at Screening.
- I.6 Subject has a MADRS total score ≥ 22 at both Screening and Baseline.
- I.7 Subject has an YMRS total score ≤ 12 at Screening.
- I.8 Female subjects of childbearing potential must have a negative serum β -hCG test at Screening.
- I.9 Females who participate in this study must be one of the following:
 - Unable to become pregnant (eg, postmenopausal, surgically sterile, etc)
 - Practicing abstinence or part of an abstinent lifestyle

Document:

Author:

Version Number:

V2.0

Version Date:

21MAY2020

Template No: CS_TP_BS016 Revision 4
Effective Date: 01Apr2016

Reference: CS_WI_BS005

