E.19 Subject is considered by the Investigator to be at imminent risk of suicide or injury to self, others, or answers "yes" to "Suicidal Ideation" item 4 (active suicidal ideation with some intent to act, without specific plan) or item 5 (active suicidal ideation with specific plan and intent) on the C SSRS assessment at the Screening visit (in the past 3 months) or Baseline.

Partial or completely missing data will be handled as follows:

- I-6 and I-7: If the MADRS or YMRS score is missing at screening or baseline, the subject will be considered to have violated the eligibility criteria and hence an IPD.
- I-5: If the date of initial onset of current major depressive episode, the date will be imputed and the time since onset will be calculated using the algorithms described in [APPENDIX 2](#). If the date is completely missing, the subject will be considered to have violated the eligibility criteria and hence an IPD.

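### Moving every partial onset date to its latest possible day cannot serve the two-sided episode-duration criterion in the SAP's important-deviation check

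*SAP*

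**What the plan says.** Protocol Section 8.1, criterion 5, limits entry on both sides: "Subject's current major depressive episode is ≥ 4 weeks and less than 12 months in duration at Screening".

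SAP Appendix 7, item 0.1, makes failure of a listed entry criterion an important protocol deviation (IPD). Such subjects "will be considered IPDs whether or not an exemption was granted during the study". When the onset date of the current episode is incomplete, "the date will be imputed and the time since onset will be calculated using the algorithms described in" Appendix 2. A fully missing date is not imputed: "If the date is completely missing, the subject will be considered to have violated the eligibility criteria and hence an IPD".

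Appendix 2 has one rule for each type of partial onset date. With the month known: "If only day unknown, impute as the earlier of: last day of the month, or date of ICF". With only the year known: "If both month and day unknown, impute as the earlier of: 31st December of the year, or date of ICF".

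SAP Section 11.1 derives the descriptive time since onset of the current episode as ("Date of informed consent – date of initial onset of current episode of major depression) / 30.25". In the same section, time since onset of the disorder is ("Date of informed consent – date of initial onset of bipolar disorder) / 365.25".

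Under SAP Section 5.2, IPDs judged able to influence the reading of the primary endpoint define the per-protocol population. Sections 16.1.5.2 and 16.2.5 repeat the primary and secondary analyses in it.

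**The concern.** The latest possible onset gives the shortest possible episode. That is strict against a minimum duration and lenient against a maximum. Because criterion 5 has both, the rule errs at each end: it can mark an eligible subject as under 4 weeks, and it can let an episode beyond 12 months through. The direction is fixed in advance, so the errors do not average out across subjects.

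At stake are the count of eligibility deviations, possibly who is in the per-protocol population, and the baseline row for time since onset of the current episode, which uses the same imputed dates.

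**Working it through.** **Inputs.** Limits of at least 28 days and less than 12 months (Protocol 8.1). Imputed onset = the earlier of the end of the month or year and the consent date (SAP Appendix 2). Duration = consent date minus onset date. The calendar dates below are illustrative; the documents give no subject-level dates.

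**Worked cases**

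1. Onset 2019 (year only), consent 15 June 2019. The earlier of 31 December 2019 and 15 June 2019 is the consent date, so the duration is 0 days and the subject fails. Consent is day 166 of the year, so there are 166 consistent dates, with durations from 0 to 165 days. Those up to 18 May (day 138) give at least 28 days. So 138 of 166 consistent dates are eligible, yet the subject fails. The same 0 days results for any consent date when only the consent year is known.
2. Onset February 2019, consent 20 March 2019. Imputed to 28 February: 20 days, fails. Possible range: 20 to 47 days.
3. Onset 2018 (year only), consent 28 December 2019. Imputed to 31 December 2018: 362 days, passes. From 1 January 2018 the duration is 365 + 361 = 726 days. Only 29, 30 and 31 December 2018 fall within 12 calendar months of consent: 3 of 365 consistent dates.
4. Onset March 2018, consent 15 March 2019. Imputed to 31 March 2018: 349 days, passes. From 1 March 2018: 379 days.

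**Rates per subject with a partial date.** These are by enumeration, assuming every consent date from 1 July 2018 to 30 June 2019 and true onset uniform over the stated number of days before consent. The 12-month limit is taken as 12 × 30.25 = 363 days.

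| Known part of date | Eligible episode flagged as under 4 weeks | Over-long episode passes (onset 0 to 548 days back) | Over-long episode passes (onset 0 to 730 days back) |
|---|---|---|---|
| Month and year | 4.4% | 7.0% | 3.5% |
| Year only | 53.7% | 73.6% | 48.9% |

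With the limit at 12 × 30.4375 = 365.25 days, the over-long rates become 8.5% and 74.4% (548 days) or 4.3% and 49.7% (730 days). No episode truly under 4 weeks passes under the written rule, because the imputed duration never exceeds the true one.

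**Divisor.** 365.25 / 12 = 30.4375. Dividing by 30.25 instead inflates months by 30.4375 / 30.25 = 1.006, or 0.6%. An episode of 363 days becomes 363 / 30.25 = 12.00 months rather than 363 / 30.4375 = 11.93.

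**The case against.** The strongest reply is that the imputed date does not decide matters alone.

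- Appendix 7 identifies violators first from the inclusion/exclusion CRF pages; other data are supporting.
- The IPD team looks at all cases and may change the programming criteria before hard lock. A 0-day duration from a year-only date would be visible in its listings.
- Appendix 7 makes a fully missing date an automatic IPD but has no matching sentence for a partial one.
- Per-protocol exclusion also needs a judgement about the effect on the primary endpoint.
- The large rates need a year-only onset for an episode that the investigator had to confirm and document. The over-long rates also presuppose that such subjects were randomized.

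All of this stands, and it limits the effect. It does not make the written rule sound. Appendix 7 sends partial dates through Appendix 2 and calculates a duration from them, so the misleading duration is the starting point that reviewers would have to correct.

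A reader might infer that the 30.25 divisor helps cause these errors. It does not. It lengthens computed durations, so it works against both, and replacing it alone would raise over-long passes (7.0% to 8.5% with the month known). Nor does the SAP say that the criterion 5 check uses it: Appendix 7 cites only Appendix 2, which has no conversion to months.

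A reader might also infer an effect on the primary result. SAP Section 5.1 keeps subjects in the ITT population whatever their deviations, and Section 7.4 leaves the per-protocol analysis outside the Hochberg procedure.

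**Conclusion.** The rule is wrong as written, with limited consequences. For a year-only onset in the consent year, failure of the 4-week limit is certain by arithmetic. For a prior-year onset, an episode of nearly two years can compute as under 12 months. With the month known, the errors are a few percent per affected subject under the assumed uniform onsets. With only the year known, they are around half or more.

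The documents give neither the number of partial dates nor the split between the two types, so no number of misclassified subjects can be stated. If partial dates are rare, the practical effect is small. The effect reaches IPD counts, possible per-protocol membership and one baseline row. Enrolment, the ITT population and the primary test are unaffected. It would go too far to say that eligible subjects will be removed from the per-protocol population, since eligibility answers and blinded review may restore them.

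The 30.25 divisor is a separate, minor inconsistency of 0.6% in a descriptive summary.

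**What to change.** **SAP Appendix 7, criterion 5.** Compute the duration from both the earliest and the latest onset consistent with the partial date, capped at consent.

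- Flag an IPD automatically only when no consistent date satisfies the criterion.
- Where some consistent dates pass and others fail, list the subject for blinded IPD review beside the recorded inclusion answer.

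The listing is essential. If the latest date qualifies, the automatic rule cannot flag the subject, so it flags only a subset of those flagged now and catches no additional over-long episodes. Cases 3 and 4 above would reach review only through the listing.

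A midpoint date is not a substitute for this check. Using the 15th of the month or 1 July with 30.4375, the same enumeration (onset 0 to 548 days back) cuts false 4-week flags to 1.0% (month known) and 13.4% (year only). But it flags 1.1% and 13.5% of eligible episodes as 12 months or more, and it passes 14.9% and 46.4% of episodes truly under 4 weeks.

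**SAP Section 11.1.** Divide by 30.4375.

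**Cost.** A few lines of SAP text and program, and no new data. The downside is small: ambiguous cases need manual review, and some episodes truly under 4 weeks, all flagged by the present rule, would be listed rather than flagged automatically.
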